16.0 Statistical Considerations and Methodology

16.1 Overview

This is a phase I/II study. The phase I portion is designed to determine the maximally tolerated dose (MTD) and toxicity profile of lenalidomide in combination with dexamethasone plus anakinra in patients with high risk SMM, IMM, or newly diagnosed multiple myeloma using the standard cohort 3+3 design. The MTD may not be reached and therefore the maximum administered dosage (MAD) will be obtained. The phase II portion is a randomized study designed to compare time to disease progression (TTP) of lenalidomide and dexamethasone plus placebo (standard treatment arm) versus lenalidomide and dexamethasone plus anakinra (experimental arm) in patients with high risk (monotypic plasma cell S-phase \geq 0.3%) SMM, IMM, or newly diagnosed multiple myeloma. Approximately one third of newly diagnosed multiple myeloma patients are expected to be high risk.

16.11 Primary Endpoint

The primary endpoint of the phase I portion is toxicity, and more specifically, MTD determination. The primary endpoint of the phase II portion of this study is time to disease progression (TTP), which will be compared between the two arms. Time to progression is defined as the time from registration until the earliest date of documentation of disease progression. If a patient dies without a documentation of disease progression, the patient will be considered to have had disease progression at the time of their death unless there is sufficient documented evidence to conclude no progression occurred prior to death. If a patient receives subsequent treatment before disease progression, they will be censored on the date of the last disease assessment. All patients meeting the eligibility criteria who have signed a consent form and have begun treatment will be evaluable for the primary endpoint.

16.12 Sample Size

The phase I portion of the trial is expected to require at least 12 patients and as many as 18 patients to determine the MTD. The phase II portion of this study is expected to accrue a maximum of 45 evaluable patients in each arm unless undue toxicity is encountered. We anticipate accruing 12 additional patients (2 phase I, 5 phase II in each arm) to account for ineligibility, cancellation, major treatment violation, or other reasons. Therefore, this study is expected to accrue a maximum of 120 patients overall.

16.13 Accrual Rate and Study Duration

The anticipated accrual rate is 4 patients per month assuming that approximately one third of newly diagnosed patients will be high risk. At this rate, it will likely take about 2.5 months to enroll, treat, and evaluate each cohort in the phase I portion of this study. The phase I portion is expected to take between 10 and 15 months. The phase II portion of this study is expected to accrue in 2 years. The total study duration is expected to be approximately 5.5 years, or until the last patient accrued has been observed for at least 2 years.

Phase I Portion

16.2 Study Design

The phase I study is designed to determine the maximally tolerated dose (MTD) and toxicity profile of lenalidomide in combination with dexamethasone and anakinra in patients with high risk SMM, IMM, or newly diagnosed multiple myeloma using the

standard cohort 3+3 design. Three patients will be treated at each dose level and observed for a minimum of four weeks (i.e. one full cycle) before new patients are treated. Doses will not be escalated in any individual patient.

16.21 MTD Definition

MTD is defined as the dose level below the lowest dose that induces dose-limiting toxicity (DLT) in at least one-third of patients (at least 2 of a maximum of 6 new patients). A total of 6 patients treated at the MTD will be sufficient to identify common toxicities at the MTD. For instance, those toxicities with an incidence of at least 25% will be observed with a probability of at least 82% ($1-(1-0.25)^6$).

If all dose levels are determined to be safe, then the maximum administered dosage (MAD) will be the dose level selected to be brought forward to the phase II portion of the study.

Refer to Section 7.22 for definition of dose-limiting toxicity (DLT).

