16.22 MTD Determination

Dose Escalation: The phase I portion of this study will utilize a standard cohort-of-three design. The dose levels to which patients will be assigned in sequential cohorts are described in Section 7.21. The first cohort of three patients will be treated at dose level 1. Decisions on when and how to dose escalate are described below.

- 16.221 Three patients will be treated at a given dose level combination and observed for one (1) cycle to assess toxicity.
- 16.222 If DLT is not seen in any of the 3 patients, 3 new patients will be accrued and treated at the next higher dose level. If DLT is seen in 2 or 3 of 3 patients treated at a given dose level, then the next 3 patients will be treated at the next lower dose level, if only 3 patients were enrolled and treated at this lower dose level.
- 16.223 If DLT is seen in 1 of 3 patients treated at a given dose level, up to 3 additional patients will be enrolled and treated at the same dose level. If DLT is seen in at least one of these additional three patients (≥ 2 of 6), the MTD will have been exceeded and further accrual will cease to this cohort. If dose-limiting toxicity (DLT) is not seen in any of the three additional patients, 3 new patients will be accrued and treated at the next higher dose level.
- 16.224 After enrolling 6 patients on a specific dose level, if DLT is observed in at least 2 of 6 patients, then the MTD will have been exceeded and defined as the previous dose unless only 3 patients were treated at the lower dose level. In that case, 3 additional patients will be treated at this lower dose level such that a total of 6 patients are treated at the MTD to more fully assess the toxicities associated with the MTD.
- 16.225 **Dose de-escalation:** If dose-limiting toxicity meets the stopping boundaries set by the above dose escalation algorithm at dose level 1 (for example, more than 1 out of 3 patients or more than 1 out of 6 patients), the study will be temporarily closed. Further dose re-escalation will depend on the toxicity profile observed, and re-evaluation of the regimen by the study team may be done.
- 16.226 If a patient fails to complete the first cycle of treatment for reasons other than toxicity, the patient will be regarded as inevaluable and will

be replaced. If a patient has a dose reduction to <70% of the expected dose or dose delay of more than 3 weeks during Cycle 1 for reasons other than DLT, the patient will be replaced by an additional patient.

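### The six-patient provision covers only the MTD, so the top anakinra level can go to Phase II as the MAD on 3 patients, below the Phase I size and duration that the plan expects

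*Combined protocol and SAP*

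**What the plan says.** Section 7.21 lists three anakinra levels, and level 3 is the highest. Section 16.21 gives two routes to the Phase II dose. In the first, "MTD is defined as the dose level below the lowest dose that induces dose-limiting toxicity (DLT) in at least one-third of patients". In the second, where no level fails, "If all dose levels are determined to be safe, then the maximum administered dosage (MAD) will be the dose level selected" for Phase II.

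The six-patient statements belong to the first route. Section 16.21 says "A total of 6 patients treated at the MTD will be sufficient to identify common toxicities at the MTD" and supports this with an 82% chance of seeing a toxicity of 25% incidence. Section 16.224 expands the level below a failed one, "such that a total of 6 patients are treated at the MTD to more fully assess the toxicities associated with the MTD".

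The escalation steps are in 16.222 and 16.223. After a clean cohort, "If DLT is not seen in any of the 3 patients, 3 new patients will be accrued and treated at the next higher dose level". After 1 of 3, as many as three more patients are treated, and escalation follows "If dose-limiting toxicity (DLT) is not seen in any of the three additional patients".

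On size, 16.12 says that Phase I is "expected to require at least 12 patients and as many as 18 patients to determine the MTD". On time, 16.13 says "it will likely take about 2.5 months to enroll, treat, and evaluate each cohort" and expects Phase I to last 10 to 15 months.

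**The concern.** Level 3 has no level above it, so it can never meet the MTD definition and can go forward only as the MAD. Section 16.224 cannot reach it, because that rule needs a failed level above. Section 16.223 adds patients only after 1 of 3 DLTs. After 0 of 3 at level 3, the only instruction is to move to a higher level, and there is none. Sections 7.2, 16.1 and 16.2 add no patient minimum for the MAD.

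The number of patients behind the Phase II dose therefore depends on the route: 6 for an MTD, but 3 or 6 for a MAD. Section 1.5 says that no trial of the three drugs together has been reported. About 50 of the 100 planned Phase II registrations (45 evaluable plus 5 extra per arm, 16.12) would receive anakinra at the selected level. What is at stake is the amount of safety information when the dose is selected, and a Phase I size and duration that the written rules can undercut.

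**Working it through.** **The plan's own figures reproduce.**
- Detection with 6 patients: 1 − 0.75^6 = 0.822, the 82% of 16.21.
- Escalation probability: e(p) = (1−p)^3 + 3p(1−p)^5 gives 0.906, 0.709, 0.494, 0.309 and 0.172 at 10, 20, 30, 40 and 50%. These match all five entries in 16.227.
- Size and duration: 3+3+6 = 12 patients, or 4 cohorts × 2.5 = 10 months. 6+6+6 = 18 patients, or 6 × 2.5 = 15 months. These are the stated ranges, which suggests that six at the top level was intended.

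**The all-clean path as written.** 0/3, 0/3, 0/3 gives 3+3+3 = 9 patients and 3 × 2.5 = 7.5 months. That is 3 patients and 2.5 months below the stated minimum. Replaced inevaluable patients are not counted.

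**Information at the selected level.**
- Detection with 3 patients: 1 − 0.75^3 = 0.578, against 0.822 with 6.
- One-sided 95% upper bound on the DLT rate: 1 − 0.05^(1/3) = 63% after 0/3, and 1 − 0.05^(1/6) = 39% after 0/6.

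**How often a MAD would rest on 3 patients.** The documents give no DLT rate per level, so the rates below are assumptions. The chance is e(p1) × e(p2) × (1−p3)^3. The all-clean chance is the product of (1−p)^3 over the three levels.

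| Assumed rates, levels 1/2/3 | e(p1) | e(p2) | (1−p3)^3 | MAD on 3 | All-clean, 9 patients |
|---|---|---|---|---|---|
| 5/5/5% | 0.973 | 0.973 | 0.857 | 81% | 63% |
| 10/10/10% | 0.906 | 0.906 | 0.729 | 60% | 39% |
| 5/10/20% | 0.973 | 0.906 | 0.512 | 45% | 32% |
| 10/20/30% | 0.906 | 0.709 | 0.343 | 22% | 13% |

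**Chance of selecting a dose with fewer than 12 patients.** Besides the all-clean path, an MTD at level 1 can be reached with 9 patients. This needs at most 1 of 6 DLTs at level 1 and at least 2 of 3 at level 2. For 10/20/30% it is 0.886 × 0.104 = 0.092.

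Section 16.223 can also be read so that accrual to a cohort stops at the second DLT. Level 2 may then end with 4 or 5 patients, for totals of 10 or 11. For 10/20/30% this adds 0.886 × 3(0.2)(0.8)^2 × (0.2 + 0.8 × 0.2) = 0.886 × 0.138 = 0.122.

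| Assumed rates | Current rules, 3 always added | Current rules, stop at second DLT | Six at MAD, 3 always added | Six at MAD, stop at second DLT |
|---|---|---|---|---|
| 5/5/5% | 64% | 65% | 0.7% | 2.0% |
| 10/10/10% | 41% | 45% | 2.5% | 6.6% |
| 5/10/20% | 35% | 39% | 2.7% | 7.2% |
| 10/20/30% | 22% | 34% | 9.2% | 21.5% |

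The reading of 16.223 does not affect the chance of a MAD on 3 patients.

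**Effect on the decision at level 3.** Level 3 clears with probability e(p) now, and with probability (1−p)^6 + 6p(1−p)^5 if six are always treated. At true rates of 20, 30 and 40% this is 71, 49 and 31% now, against 66, 42 and 23%: a change of 5 to 8 points.

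**The case against.** The plan nowhere states that Phase II may open on 3 patients. A reader might infer that the sponsor chose this. The documents do not support that: 16.21 requires every level to be found safe without defining how, the rules simply run out after 0/3 at level 3, and the stated 12 to 18 patients fit six at the top level. An omitted sentence is the likelier explanation. It still leaves nothing in the rules that requires six.

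The 12 patients are also an expectation, worded for determining the MTD. A path that finds no MTD does not strictly contradict it, and even with six at the MAD, 12 is not a floor. That stands, so this is a mismatch between planning figures and rules, not an arithmetic error.

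The effect on safety is moderate. Patients at levels 1 and 2 receive the same three drugs with the same amount of anakinra per injection, less often, and so carry some information about level 3. In Phase II, 16.362 suspends accrual if 3 of the first 12 treated patients have related grade 4 or higher non-hematologic events. It is applied to each arm separately, and the DSMB reviews safety at least twice a year. This limits the consequence. It does not remove it, because that rule acts after the dose is chosen and does not count hematologic events.

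Lastly, an added cohort may be hard to supply. The Phase I notes in the Schema and in 13.0 say that anakinra is no longer provided and that all patients go off study treatment, and 19.2 repeats the supply change. This bears on which fix is practical.

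**Conclusion.** The gap is real. As written, a MAD can rest on 3 patients, with 58% rather than 82% detection of a 25% toxicity at that level, and the all-clean path ends at 9 patients and about 7.5 months. These figures follow from the plan's own rules. The 22 to 81% chance of a MAD on 3 patients rests on assumed DLT rates, and the figures for fewer than 12 patients depend also on how 16.223 is read.

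Two stronger readings fail. A reader might infer that the 82% is wrong. It is correct for six patients at the MTD, and the plan does not claim it for a MAD. A reader might also infer that the gap makes an unsafe dose likely to go forward. The change of 5 to 8 points in clearance does not show that, and at the low assumed rates clearing level 3 is the right decision. What is lost there is precision and toxicity detection at the point of dose selection.

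**What to change.** Reconcile 16.12, 16.13, 16.21 and 16.22 on the number of patients at the MAD, in one of two ways.

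1. Extend the existing six-patient provision and the 2-of-6 rule to the MAD. The all-clean path becomes 3+3+6 = 12 patients and about 10 months, and the maximum stays at 18 patients and 15 months.
2. Keep 3 patients, restate the expected minimum as 9 patients and about 7.5 months, and say that the 82% does not apply to a MAD resting on 3, where the figure is 58%.

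In either case, say that 12 is an expectation and not a floor, and state how many evaluable patients were actually treated at the MAD before Phase II opens. The documents do not report that number.

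The cost is wording only if six were already treated at level 3. Otherwise the first option adds 3 patients and about 2.5 months. If the expansion takes level 3 to 2 of 6 and level 2 must then be expanded, it adds about 6 patients and 5 months. Because anakinra is no longer provided, the second option is then the cheap fix.

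As an editorial matter, MAD is spelled out in two ways (7.2 against 16.1 and 16.21), and one should be used throughout.

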16.22 MTD Determination

Dose Escalation: The phase I portion of this study will utilize a standard cohort-of-three design. The dose levels to which patients will be assigned in sequential cohorts are described in Section 7.21. The first cohort of three patients will be treated at dose level 1. Decisions on when and how to dose escalate are described below.

- 16.221 Three patients will be treated at a given dose level combination and observed for one (1) cycle to assess toxicity.
- 16.222 If DLT is not seen in any of the 3 patients, 3 new patients will be accrued and treated at the next higher dose level. If DLT is seen in 2 or 3 of 3 patients treated at a given dose level, then the next 3 patients will be treated at the next lower dose level, if only 3 patients were enrolled and treated at this lower dose level.
- 16.223 If DLT is seen in 1 of 3 patients treated at a given dose level, up to 3 additional patients will be enrolled and treated at the same dose level. If DLT is seen in at least one of these additional three patients (≥ 2 of 6), the MTD will have been exceeded and further accrual will cease to this cohort. If dose-limiting toxicity (DLT) is not seen in any of the three additional patients, 3 new patients will be accrued and treated at the next higher dose level.
- 16.224 After enrolling 6 patients on a specific dose level, if DLT is observed in at least 2 of 6 patients, then the MTD will have been exceeded and defined as the previous dose unless only 3 patients were treated at the lower dose level. In that case, 3 additional patients will be treated at this lower dose level such that a total of 6 patients are treated at the MTD to more fully assess the toxicities associated with the MTD.
- 16.225 **Dose de-escalation:** If dose-limiting toxicity meets the stopping boundaries set by the above dose escalation algorithm at dose level 1 (for example, more than 1 out of 3 patients or more than 1 out of 6 patients), the study will be temporarily closed. Further dose re-escalation will depend on the toxicity profile observed, and re-evaluation of the regimen by the study team may be done.
- 16.226 If a patient fails to complete the first cycle of treatment for reasons other than toxicity, the patient will be regarded as inevaluable and will

be replaced. If a patient has a dose reduction to <70% of the expected dose or dose delay of more than 3 weeks during Cycle 1 for reasons other than DLT, the patient will be replaced by an additional patient.

- 16.227 Operating Characteristics for standard cohort of 3 design: The following table gives the probability of dose escalation at a single dose level as a function of the true probability of DLT at that level using the cohorts of 3 design described above.

True Rate of DLT (%)	Probability of Dose Escalation
10	0.91
20	0.71
30	0.49
40	0.31
50	0.17

16.23 Analysis Plans

All the relevant results pertaining to toxicity, MTD, response, timed endpoints and laboratory correlates will be examined in an exploratory and hypothesis-generating fashion. The small sample size and the heterogeneous patient population associated with phase I studies restricts the generalizability of the results. Any notable statistical result should only be viewed as preliminary evidence for further study in Phase II trials rather than a definitive finding in and of itself. Data will continue to be collected on patients as long as they are trial participants.

16.231 Adverse Events Profile

The number and severity of all adverse events (overall and by dose-level) will be tabulated and summarized in this patient population. The Grade 3+ adverse events will also be described and summarized in a similar fashion. This will provide an indication of the level of tolerance for this treatment combination in this patient group.

16.232 Toxicity Profile

The term toxicity is defined as adverse events that are classified as either possibly, probably, or definitely related to study treatment. Non-hematologic toxicities will be evaluated via the ordinal CTC standard toxicity grading. Hematologic toxicity measures of thrombocytopenia, neutropenia, and leukopenia will be assessed using continuous variables as the outcome measures (primarily nadir) as well as categorization via CTC standard toxicity grading.

Overall toxicity incidence as well as toxicity profiles by dose level, patient and tumor site will be explored and summarized. Frequency distributions, graphical techniques and other descriptive measures will form the basis of these analyses.

16.233 Response Profile

A response is defined to be a sCR, CR, VGPR, or PR noted as the objective status. Response will be evaluated using all cycles of treatment. All patients meeting the eligibility criteria who have signed

a consent form and have begun treatment will be evaluable for response.

Responses will be summarized by simple descriptive summary statistics delineating complete and partial responses as well as stable and progressive disease in this patient population.

Phase II Portion

16.3 Statistical Considerations

16.31 Study Design:

In a study of consecutive patients treated with lenalidomide and dexamethasone as initial therapy for symptomatic multiple myeloma at Mayo Clinic, the TTP for 16 high risk patients (defined as presence of hypodiploidy, del(13q) by metaphase cytogenetics, del(17p), IgH translocations [t(4; 14), or t(14;16)] or PCLI $\geq 3\%$) was approximately 18 months (Kapoor et al, 2009). However, that definition of high risk may not be inclusive of all patients that will be accrued to this study. In addition, a second study of patients treated with lenalidomide and dexamethasone at Mayo Clinic estimated that 29 high risk patients (defined as PCLI $\geq 1\%$) had a median TTP of approximately 29 months (unpublished). This study will define high risk as monotypic plasma cell S-phase $\geq 0.3\%$. PCLI and monotypic plasma cell S-phase are both assays that measure plasma cell proliferation, where a cutoff of $\geq 0.3\%$ for monotypic plasma cell S-phase would give a similar patient population as using a cutoff of $\geq 1\%$ for PCLI. Thus, estimates of TTP from previous studies that defined high risk using PCLI would still be relevant. However, due to the small sample sizes and inconsistency in TTP estimates for high risk patients in these prior studies, the lenalidomide and dexamethasone arm of this study will be used to better estimate TTP in high risk myeloma patients (defined as monotypic plasma cell S-phase $\geq 0.3\%$ for this study). We estimate that the median TTP in the lenalidomide and dexamethasone plus placebo arm will be 20 months. We are interested in testing the alternative hypothesis that the median TTP in the lenalidomide and dexamethasone plus Anti-IL-1 antibody arm will be at least 40 months. This translates into an improvement in the 2-year TTP from 43% to 66% assuming an exponential survival model.

The primary goal of this trial is to compare the time to progression of the standard treatment arm (Arm A) to the experimental arm (Arm B). We will conduct a randomized trial comparing the experimental arm against the standard treatment arm. We will enter 45 evaluable patients to each arm of the study using a 1:1 randomization scheme (Pocock et al, 1975). The stratification factors that will be used are listed in Section 5.0. The primary analysis will be a comparison of Arm A to Arm B using a one-sided log-rank test between the two Kaplan-Meier curves. This final analysis will take place after an approximate 24-month accrual period and after 52 total progressions have occurred or the last patient has been followed for at least 2 years (whichever occurs first). Additionally, we assume a constant accrual rate over the course of the study and that we will not have a significant lost to follow-up issue, as historically lost to follow-up rates in Mayo clinic trials have been $< 1\%$. A sample size of 45 evaluable patients per arm (90 total) provides 80% power to detect an improvement in median time to progression from 20 months to 40 months (a hazard ratio of 2.0), using a 1-sided log-rank test at a significance level of 0.05. A final decision regarding the level

of promise for the experimental regimen will take all factors into account including TTP, response rate, OS, adverse events, and other relevant factors. All patients meeting the eligibility criteria who have signed a consent form and have begun treatment will be evaluable for the primary endpoint.

